7.3 OR1 Population

Missing primary endpoint data will be imputed using MI, as described above. For all other endpoints, only observed data will be used for the OR1 population.

8 Definition of Endpoints

8.1 Safety Endpoints

Following are the study's safety endpoints:

• Incidence of adverse events (AEs) including serious adverse events (SAEs) from implantation to 12-months post-activation.

8.2 Primary Efficacy Endpoints

Document ID	Revision / Date	Page
G02-CLP-0009	Rev. 06 / 18 May 2022	12 of 26

The study's primary efficacy endpoint for each subject is response at 6 months post system activation as demonstrated by ≥50% improvement in the average number of urgency-related incontinence episodes as compared to baseline, measured by 7-day Patient Voiding Diary. Specifically, the primary endpoint will be defined as follows:

Success ("1") If the percent change from baseline to 6 months post system

activation in urgency-related incontinence episodes ≥50%

Failure ("0") Otherwise

Where the percent change from baseline to 6 months post system activation in urgency-related incontinence episodes is calculated as follows:

Document ID	Revision / Date	Page
G02-CLP-0009	Rev. 06 / 18 May 2022	13 of 26

$$\% \ Change_{BL \ to \ 6-months} = \frac{Episodes_{Avg. \ at \ BL} - \ Episodes_{Avg. \ at \ 6-months}}{Episodes_{BL}} * 100\%$$

where the average number of episodes is the average number of urgency-related leaks per day over the 7- day voiding diary. In the case that fewer than 5 days of diary data are available, then the average number of episodes for the given time point will be considered missing and, consequently, the primary endpoint will also be considered missing.

For the primary efficacy analysis, missing data will be addressed using the multiple imputation (MI) method, described above (Section 7.1).

Note: continuous score will be MI-imputed, and then the response is defined.

8.3 Secondary Efficacy Endpoints

The following will be assessed as formal secondary efficacy endpoints

 Proportion of subjects with ≥10 points (MID) improvement compared to baseline in HRQL (based on OAB-q) at 6 months post system activation

This endpoint is defined dichotomously as follows:

Success ("1") If the absolute improvement (increase) in HRQL from baseline is ≥10 points (MID)

Failure ("0") Otherwise

Proportion of responders at 12 months post system activation as demonstrated by ≥50% improvement in either average number of urgency related incontinence episodes or average number of large (severe) urgency related incontinence episodes, as measured by 7-day Patient Voiding Diary.

This endpoint is defined dichotomously as follows:

Success ("1") If the percent reduction in either average number of urgency-related leaks per day *or* average number of large urgency-related leaks per day from baseline to 12 months follow-up is ≥50%

Failure ("0") Otherwise

Proportion of responders at 6 months post system activation as demonstrated by ≥50% improvement in the average number of moderate-severe urgency episodes PPIUS degree 3,4 or <8 voids/day

This endpoint is defined dichotomously as follows:

Success ("1") If either the percent reduction in average number of moderate-severe urine

Document ID	Revision / Date	Page
G02-CLP-0009	Rev. 06 / 18 May 2022	14 of 26

output episodes with PPIUS degree 3,4 per day (i.e. average number urine output episodes with urgency level above 2) from baseline to 6 months is \geq 50% **or** the average number of total voids per day is less than 8 at 6 months

Failure ("0")

Otherwise

This endpoint is defined only for patients with baseline number of voids per day of at least 8 and baseline number of urgent episodes (PPIUS 3 or 4) of at least 9 per 7-day diary.

Missing data for the secondary endpoints will be imputed according to Section 7.1, above.

8.4 Additional Efficacy Endpoints

The following additional efficacy endpoints will be assessed based on the data summarized in the data management reports:

- Patient Global Impression of Improvement (PGI-I) score
- Treatment Benefit, Satisfaction, and Willingness to Continue (BSW)
- Improvement in OABq (HRQL (and its subscales) and symptoms severity)
- Changes in the following OAB symptoms as measured by voiding diary 6 and 12-months post system activation compared to baseline:
 - o Reduction in the average number of severe/large urgency related incontinence episodes
 - o Reduction in the number of micturition episodes.
 - o Reduction in the number of urgency related incontinence episodes.
 - Reduction in degree of urgency prior to void on Patient Perception of Intensity of Urgency Scale (PPIUS) from 0-4.
 - o Reduction in severity of incontinence episodes (amount leaked).
- Proportion of dry subjects following treatment with the RENOVA iStim System as measured by 3
 consecutive days of a patient voiding diary.
- Assessment of fecal incontinence symptoms in patients suffering from mixed fecal and urine incontinence.
- Device usage
- Patient compliance with treatment through 6-months

Instructions for Diary calculation are as detailed in the appendix to the SAP.

9 Sample Size Considerations

The sample size for the primary endpoint was calculated using PASS 2015 software by a one-sided exact test for a single binomial population, under the following assumptions:

Document ID	Revision / Date	Page
G02-CLP-0009	Rev. 06 / 18 May 2022	15 of 26

- Significance level = 0.025 (one-sided)
- Power ≥ 80%
- Assumed treatment success rate at 6 months = 65%
- Prespecified performance goal = 50%.

Given these assumptions, 114 evaluable subjects are required. A total of 134 enrolled subjects, accounting for 15% attrition, is sufficient to evaluate the primary endpoint. However, this sample size is not adequate to evaluate all secondary objectives with sufficient power – specifically the following important secondary objective:

To demonstrate the proportion of responders at 6 months post system activation, defined by ≥50% improvement in the average number of moderate-severe urgency episodes PPIUS degree 3,4 or <8 voids/day, is greater than 45%.

This endpoint is defined only for patients with baseline number of voids per day of at least 8 and baseline number of urgent episodes (PPIUS 3 or 4) of at least 9 per 7-day diary. It is expected that 70% of enrolled subjects will meet these criteria.

Sample size requirements to evaluate this secondary endpoint are calculated in the same manner as the primary, under the following assumptions:

- Significance level = 0.025 (one-sided)
- Power ≥ 85%
- Assumed treatment success rate at 6 months = 61%
- Prespecified performance goal = 45%

A total of 89 evaluable subjects are required. Assuming 15% attrition rate, a total of 105 subjects meeting the criteria described above is needed. With 70% of enrolled subjects meeting the analysis criteria, 150 total sample size is sufficient to evaluate the secondary endpoint.

The total sample size for the OASIS trial is 150 subjects.

10 Data Derivation and Transformation

Data not specifically recorded on a CRF will be derived as follows:

- Study Duration [days] = Date of Last Visit Date of First Visit + 1.
- HbA1c values will be reported in units of mmol/mol. For cases of HbA1c reported in percentage, the following conversion formula will be used:

Document ID	Revision / Date	Page
G02-CLP-0009	Rev. 06 / 18 May 2022	16 of 26

HbA1c (mmol/mol) = $[HbA1c (\%) - 2.15] \times 10.929^{1}$

- Coding of Adverse Events will be done using the most recent MedDRA version.
- Coding of Concomitant Medication will be done using the most recent WHO Drug dictionary version.
- Baseline will be defined as the value at the "Enrollment and Screening" visit unless noted otherwise.
- OAB duration at baseline from Date of OAB Diagnosis [years] = Date of Screening Date of OAB Diagnosis/365.25.
- Partial dates that are required for analysis will be imputed in the following fashion:
 - o Dates with missing month and day will be imputed as July 1st.
 - o Dates with missing day only will be imputed as the 15th of the month.
- Since querying of paper diaries is not possible at the time of completion and not feasible in an accurate
 manner afterwards, no query management process is used for the paper diaries. In its place a set of
 automatic rules will be applied to correct discrepancies in the paper diaries, as detailed in the appendix
 to the SAP.

11 Interim Analysis

An administrative interim analysis is required at the time one-month data is available on 50 implanted subjects. This analysis is intended to support necessary company financing activities, and visibility of the results will be restricted to only those involved in those activities. Importantly, no person – BlueWind employee or consultant – who has interaction with investigational sites will have visibility to interim results. The interim analysis does not require subsequent adjustment of the overall trial significance level (0.025) to account for type I error inflation because:

- it is administrative in nature only, with limited distribution
- it is looking primarily at 1-month data, which may not be reflective of the primary endpoint at 6 months
- the interim look is at the time 1/4 to 1/3 of the total number of enrolled subjects is 1/6 of way (1 month follow-up) toward the primary effectiveness endpoint (at 6 months follow-up). This represents 1/18th to 1/24th of the total trial information. Under an O'Brien alpha spending function, virtually zero alpha would be allocated to the interim analysis
- there is no opportunity to terminate the trial early for effectiveness.

Only data from the first 50 subjects with one-month data will be reviewed. Data from enrolled subjects that do not yet have 1-month data available will be excluded from the analysis. All data from the 50 subjects will be included in the review (i.e. data from follow-up visits subsequent to the 1-month visit will also be summarized, if available). The interim analysis will be performed on the PP population, and MI will not be employed.

The analysis will involve, in summary form, results on:

- device- and procedure-related adverse events
- percent improvement in the average number of urgency-related incontinence episodes, as compared to baseline, measured by 7-day Patient Voiding Diary. The percent change from baseline to each follow-up visit post system activation in urgency-related incontinence episodes is calculated as follows:

Document ID	Revision / Date	Page
G02-CLP-0009	Rev. 06 / 18 May 2022	17 of 26

% Change_{BL to f/u} =
$$\frac{Episodes_{Avg. at BL} - Episodes_{Avg. at f/u}}{Episodes_{BL}} * 100\%$$
,

where the average number of episodes is the average number of urgency-related leaks per day over the 7- day voiding diary.

A frequency distribution will be presented with bins defined as:

- <0.25
- ≥0.25 <0.50
- ≥0.50 <0.75
- ≥0.75
- Proportion of responders at each follow-up post system activation as demonstrated by ≥50% improvement
 in either average number of urgency related incontinence episodes or average number of large (severe)
 urgency related incontinence episodes, as measured by 7-day Patient Voiding Diary.
- Proportion of subjects with ≥10 points (MID) improvement compared to baseline in HRQL (based on OAB-q) at each follow-up post system activation
- Proportion of responders at each follow-up visit post system activation, as demonstrated by ≥50% improvement in the average number of moderate-severe urgency episodes PPIUS degree 3,4 or <8 voids/day
- Subject disposition
- Demographics
- Additional Endpoints of interest

12 Statistical Analysis

The present section details the statistical analyses to be performed. The data will be summarized in tables listing the mean, standard deviation, median, minimum, maximum and number of subjects for continuous data, or in tables listing count and percentage for categorical data where appropriate.

12.1 Subject Disposition

The following will be provided:

- Number and percent of subjects in each of the analysis populations (ITT, PP, OR1) by center and overall
- Listing of subjects excluded from each of the analysis populations along with reason for exclusion.
- Number and percent of subjects consented to the study
- · Number and percent of subjects implanted
- Subject accountability table by visit

Study termination:

Number and percent of subjects who completed the study.

Document ID	Revision / Date	Page
G02-CLP-0009	Rev. 06 / 18 May 2022	18 of 26

- Frequency of premature termination reasons
- Listing of all dropouts along with reason for termination and time of termination according to date of last study visit.

Protocol Deviations

Listing of protocol deviations.

12.2 Baseline Characteristics

Baseline characteristics will be analyzed using the ITT population.

Descriptive statistics will be provided for the following:

- Demographic characteristics (age, race (if applicable), ethnicity, weight, height, BMI, Index leg circumference). Note that ethnicity will be reported only on enrolled subjects from the US.
- Overactive bladder history, including OAB medication, previous PTNS, Botulinum toxin injections
- Frequency distribution of medications for the OAB indication
- Listing of concomitant medications at time of enrollment
- · Listing of general medical/surgical history
- Smoking history (Past/Current/No)
- Neurological Examination:
 - o Frequency distribution of evaluation (normal/abnormal/not done) at baseline

12.3 Implantation

Evaluation of implantation parameters will be assessed using the ITT population and include descriptive statistics of the following:

- Implanted leg (Right/Left)
- Use of pre-op and post-op medications (antibiotics and anti-inflammatory/analgesics)
- Preparations performed (skin scrub and anesthesia type)
- Skin to skin time (minutes)
- Implant position depth (cm)
- Final incision size (cm)
- Intraoperative test performed (Yes/No). If testing was performed then the descriptive statistics of the following will be presented:
 - Response to test stimulation (Yes/No). For cases of response, descriptive statistics of the following will also be presented:
 - Number of implant positioning performed
 - Frequency (Hz)

Document ID	Revision / Date	Page
G02-CLP-0009	Rev. 06 / 18 May 2022	19 of 26

- Pulse width (μsec)
- Amplitude (mAmp)
- Polarity
- Response type (Sensory/Motor/Both)

12.4 System Activation

System activation parameters will be summarized in tables containing descriptive statistics of the following using the ITT population:

- Parameters setting (, sensory response level, motor response yes/no, motor response level)
- Treatment settings
- Location and description of stimulation sensation
- Activation evaluation
- Treatment regimen: frequency and duration of treatment prescribed

12.5 Safety

A staged enrollment of the study is planned, with up to 30 patients enrolled in parallel with completion of additional toxicology testing. To support the planned IDE supplement to expand to full pivotal enrollment, an interim safety report will be generated when the first stage of enrollment is complete, with a maximum of 30 subjects. No primary endpoint data will be evaluated, and the data reported will be consistent with the safety data to be included in future IDE progress reports. Therefore, this does not constitute an interim analysis. All safety analyses will be performed on the ITT population.

The following will be provided:

Adverse Events:

All Adverse Events (including serious) will be tabulated in a series of frequency tables with - number of AEs, number of subjects and percentage of subjects with AE and according to :

- Severity
- o Relation to implantation procedure
- Relation to medical device
- Severity and Relation to implantation procedure
- Severity and Relation to medical device
- Body system and preferred term

A single adverse event will appear in multiple tables.

• Serious Adverse Events:

Same as the previous bullet (Adverse Events), limited to serious adverse events only.

Document ID	Revision / Date	Page
G02-CLP-0009	Rev. 06 / 18 May 2022	20 of 26

- Vital Signs (systolic and diastolic blood pressure, temperature, pulse and index leg circumference).
 Note when more than one measurement exists per visit, the average result will be used for the analysis:
 - Descriptive statistics of vital signs by visit
 - o Descriptive statistics of change from activation visit to each follow-up visit
- Physical Examination by body system:
 - o Frequency distribution of evaluation (normal/abnormal/not done) by visit
 - Shift table of normal/abnormal transitions from Implantation to all subsequent visits
 - Listings of abnormal physical examination results, including patient ID, visit, body system and abnormality description (CS/Not CS).
- Concomitant medications
 - By-subject listing of concomitant medication including subject ID, site, medication generic name or therapy, daily dose, units, route, start date, end date, whether ongoing, indication.

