10.3.3 Other Endpoints

The following endpoints will be assessed as other endpoints for the 6-, 12-, 24- and 36-months post activation, without formal hypothesis testing and type I error control.

- Incidence of procedure or device related adverse events from 12- to 36-months post activation
- Patient Global Impression of Improvement (PGI-I) score
- Treatment Benefit, Satisfaction, and Willingness to Continue (BSW)
- Reduction in the average number of severe/large urgency related incontinence episodes
- Improvement in OAB-q (HRQL and symptoms severity).
- Changes in the following OAB symptoms as measured by voiding diary compared to baseline:
 - Reduction in the number of micturition episodes.
 - o Reduction in the number of urgency related incontinence episodes.
 - Reduction in degree of urgency prior to void on Patient Perception of Intensity of Urgency Scale (PPIUS) from 0-4.
 - Reduction in severity of incontinence episodes (amount leaked).
- Proportion of dry subjects following treatment with the RENOVA iStim System as measured by 3
 consecutive days of a patient voiding diary
- Assessment of fecal incontinence symptoms in patients suffering from mixed fecal and urine incontinence
- Patient compliance with treatment
- Duration from treatment initiation to symptoms improvement (in subset of patients who stopped treatment after completing the 12-month visit and started again when consented for the long-term follow-up).
- Device usage

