11.4.6 BlueWind RENOVA iStim™ System Long-Term Follow Up (LTF) Visits – Visits 9-12

Long term follow-up visits will be performed at 18, 24, 30, 36-months post activation.

If a subject already completed the 12-months follow-up and exited the study, she will be invited for a Long-Term Follow-Up Consent Visit in which, following her consent to participate in the long-term follow-up study, some eligibility criteria will be verified and treatment parameters setting will be performed. Subjects will enter the visit schedule using their original system activation date. Any visit that has already passed will not be counted as a missed visit.

If the subject discontinued treating herself when she exited the study and is activated again she will be asked to treat herself for 30 minutes, twice a day, for at least 4 weeks prior to completing the first LTF visit. During this period, she will be asked to complete a modified daily diary to capture incontinence episodes, time to treatment effect, and symptom improvement questions.

Subjects continuing to the long-term follow-up will be asked to treat themselves per physician discretion but not less than two 30-minute treatment per week.

All follow-up visits will require completion of 3-day voiding diary by the patient before coming to visit.

Follow-up visits 10 (24-months) and 12 (36-months) will be performed in clinic and will be similar to the 6 and 12-months follow-up visits

Follow-up visits 9 and 11 will be performed over a phone call unless the treatment is not effective enough or treatment parameters are not optimal or patient is experiencing an AE or device malfunction. In such cases the patient will arrive to the clinic and a visit similar to the 1, 3, and 9- months post activation will be performed.

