13.5 Statistical Analyses

13.5.1 Overview

Analysis of subject disposition and of safety will be done on the ITT population. The primary efficacy analysis and analyses of additional endpoints will be done on ITT. Supportive efficacy analyses will be done for the primary efficacy endpoint on the PP population and for other efficacy endpoints in both ITT and PP population.

Number	Revision / Date	Page
G02-CLP-0002_US	Rev. 08 / 27 July 2021	49 of 75

The data will be summarized in tables listing the mean, standard deviation median, minimum, maximum and number of subjects for continuous data, or in tables listing count and percentage for categorical data where appropriate. Descriptive statistics will be provided by time point both numerically and graphically as appropriate. Data listing by subject will be provided.

All statistical analyses will be performed, and data appendices will be created using the SAS® system. The effects of noncompliance, dropouts, and possible covariates such as Age will be assessed to determine the impact on the general applicability of results from this study.

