13.5.6 Additional Efficacy Endpoints

The following endpoints will be assessed as other endpoints for the 6-, 12-, 24- and 36-months post activation, without formal hypothesis testing and type I error control.

- Incidence of procedure or device related adverse events from 12- to 36-months post activation.
- Patient Global Impression of Improvement (PGI-I) score.
- Treatment Benefit, Satisfaction, and Willingness to Continue (BSW).
- Reduction in the average number of severe/large urgency related incontinence episodes.
- Improvement in OAB-q (HRQL and symptoms severity) at 6- and 12- months post system activation.
- Changes in the following OAB symptoms as measured by voiding diary compared to baseline:
 - Reduction in the number of micturition episodes.
 - Reduction in the number of urgency related incontinence episodes.
 - Reduction in degree of urgency prior to void on Patient Perception of Intensity of Urgency Scale (PPIUS) from 0-4.
 - Reduction in severity of incontinence episodes (amount leaked).
- Proportion of dry subjects following treatment with the RENOVA iStim System as measured by 3
 consecutive days of a patient voiding diary.
- Assessment of fecal incontinence symptoms in patients suffering from mixed fecal and urine incontinence.
- Patient compliance with treatment.
- Duration from treatment initiation to symptoms improvement (in subset of patients who stopped treatment after completing the 12 month visit and started again when consented for the long term follow-up
- Assessment of treatment regimen

Number	Revision / Date	Page
G02-CLP-0002_US	Rev. 08 / 27 July 2021	51 of 75

Device usage

All additional efficacy endpoints will be analyzed in all three efficacy analysis sets—ITT, PP and OR1.

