18.8 Adverse Events Collection and Recording

Collection of AEs will start after the time that the informed consent form is signed and continue until the subject exits the study. AEs will be monitored throughout the study. Investigators must obtain all information available to determine the causality and outcome of the AE and to assess whether it meets the criteria for classification as a serious adverse event requiring immediate notification to the sponsor or its designated representative. All reported AEs will be documented on the appropriate eCRF and will include the event description (sign, symptom, and diagnosis), onset, resolution, seriousness, severity, cause and action taken. The investigator or an authorized designee must assess the causality and severity for all AEs. All AEs will be followed by the investigator until

Number	Revision / Date	Page
G02-CLP-0002_US	Rev. 08 / 27 July 2021	58 of 75

resolution or until the termination of the subject's study participation. Any adverse events that remain unresolved at the end of the study will be explained in the final report.

Individual symptoms should not be reported as AE, alternatively a diagnosis should be made based on the symptoms and this diagnosis should be entered under the "description/type" column.

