6.1 Safety and Efficacy Analysis Population – Intent To Treat (ITT)

The safety and effectiveness endpoints will be evaluated under principles of Intent to Treat (ITT). The analysis set will consist of all subjects for whom the implantation of the BlueWind RENOVA iStim[™] system was attempted. Specifically, the analysis set will consist of all subjects for whom skin incision time was not missing.

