Any subjects enrolled prior to the COVID-19 outbreak may be subject to telephone follow-ups instead of onsite follow-up visits for a period of time. Interactions with affected subjects, then, would be different than for those who are routinely followed in the clinic, and only a subset of data will be able to be collected. A covariate adjusted logistic regression model, as described above, will be fit to assess the potential impact of COVID-19 on study outcomes, with an indicator variable indicating subjects enrolled prior to, and after, stay- at-home policies were enacted.

Finally, a test of homogeneity of effect across investigational center will be conducted. Descriptive statistics (e.g. success rate) will be reported for every participating center. Any center enrolling fewer than five subjects will be excluded from the formal test of homogeneity. To acknowledge that this test of homogeneity is fundamentally underpowered, a significance level of 0.15 will be used to determine whether a potential differential effect across centers exists and to trigger additional, exploratory analysis to better understand the nature of the difference.

13 Long-Term Follow-Up

Upon completion of the 12-month follow-up visits, patients will enter a long-term follow-up phase. Formal study visits will occur at 24 and 36 months. Less comprehensive visits conducted via telephone will be conducted at months 18 and 30. The telephone visits will assess adverse events and subject diary data.

Document ID	Revision / Date	Page
G02-CLP-0009	Rev. 06 / 18 May 2022	24 of 26

All primary, secondary and additional efficacy measures will be summarized using appropriate descriptive statistics - mean, median, standard deviation and 95% confidence intervals for continuous measures and frequency distributions for categorical or binary data. Adverse events, and treatment regimen data will be summarized.

14 Data Listings

Data listings will be provided for all data available from the CRF.

15 Computer Software

All statistical analyses will be carried out using SAS® Version 9.4 or higher under Windows® 2016 Terminal.

Document ID	Revision / Date	Page
G02-CLP-0009	Rev. 06 / 18 May 2022	25 of 26

16 Appendix 1: Rules for Correction of Discrepancies in Paper Diaries

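### As written, the 12-36 month incidence of procedure- or device-related adverse events has the whole ITT set as denominator, so women not observed after month 12 count as event-free and dilute the rate

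*SAP*

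**What the plan says.** **Population.** SAP 12.5 states: "All safety analyses will be performed on the ITT population". Protocol 13.5.1 agrees: "Analysis of subject disposition and of safety will be done on the ITT population". SAP 6.1 fixes membership at surgery: "Specifically, the analysis set will consist of all subjects for whom skin incision time was not missing". Later follow-up plays no part in it.

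**Endpoint.** Protocol 10.3.3 lists "Incidence of procedure or device related adverse events from 12- to 36-months post activation" among the other endpoints, with no formal test. Protocol 13.5.6 repeats it in the list of additional efficacy endpoints and says of that list: "All additional efficacy endpoints will be analyzed in all three efficacy analysis sets—ITT, PP and OR1". The SAP does not list it: 8.1 ends its safety window at 12 months, and 8.4 omits it.

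**Statistic.** SAP 12.5 tabulates the number of events and the number and percentage of subjects. It gives no person-time rate, time-to-event summary or at-risk denominator. On the long-term phase, SAP section 13 says only: "Adverse events, and treatment regimen data will be summarized". It is worded as though all patients pass into that phase after month 12.

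**Who is observed.** Under Protocol 18.8, adverse event collection starts after consent and will "continue until the subject exits the study". Protocol 11.4.1 and 11.4.6 describe women who completed month 12 and exited before the long-term visits existed. They are invited back, must consent again and must pass some eligibility checks. They join the schedule by their original activation date, and "Any visit that has already passed will not be counted as a missed visit". Protocol 10.7.2 bars re-entry once the implant has been removed.

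**The concern.** An ITT denominator suits the period from implantation to month 12, when every woman is meant to be under observation. It suits months 12-36 less well, because membership was fixed at incision while observation depends on staying in the study or re-consenting. A woman with no contact after month 12 cannot contribute an event to the numerator, yet she stays in the denominator. This covers women who exited at month 12 and declined or failed re-screening, and women who left earlier.

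The dilution works in one direction only: it makes the device look safer. This is the only long-term safety endpoint listed, and the implant stays in place after the study ends (Protocol section 21). No hypothesis test depends on it, so what is at stake is an accurate description of late harm, not the trial's success criterion.

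**Working it through.** **Inputs**
- Planned enrolment: 150 (SAP section 9). Protocol 10.2.1 describes these as women in whom implantation was attempted, so 150 is taken as the approximate ITT size.
- Share of ITT with no observation after month 12: f. Neither document gives it. The 15% attrition used for sizing is not a long-term rate. I show 0-40% as an assumption.
- Number of women with a related event in months 12-36: not given; illustrative values only.

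**Reproducing the plan's own figure.** For the secondary endpoint that sets the sample size (goal 45%, assumed rate 61%, one-sided 0.025), an exact binomial test with n = 89 rejects at 50 or more responders, with alpha 0.0223 and power 0.851. Then 89/0.85 = 104.7, rounded up to 105, and 105/0.70 = 150. The stated 150 reproduces.

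**Formula.** Let p be the risk in observed women and q the risk in unobserved women.
- True incidence in ITT = (1 - f)p + fq
- Expected ITT percentage as the text reads = (1 - f)p, because unobserved women contribute no events
- If q = p, the ratio is (1 - f) and the relative understatement is f

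**Expected ITT percentage if the true incidence is 10% and q = p**

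| f | Women observed | Expected events | ITT percentage |
|---|---|---|---|
| 0% | 150 | 15.0 | 10.0% |
| 10% | 135 | 13.5 | 9.0% |
| 20% | 120 | 12.0 | 8.0% |
| 30% | 105 | 10.5 | 7.0% |
| 40% | 90 | 9.0 | 6.0% |

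**The same effect from the observed side.** Suppose nine women have a related event. On ITT that is 9/150 = 6.0%. Among women actually observed it is 9/135 = 6.7%, 9/120 = 7.5%, 9/105 = 8.6% or 9/90 = 10.0%.

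**Partial observation.** A woman followed from month 12 to month 36 contributes 24 months, or 2.0 woman-years. One who re-enters at month 24, with no recovery of events since exit, contributes 12 months, or 1.0. A percentage of subjects weights the two equally; a person-time rate does not.

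**Selection.** If a woman's implant was removed after she left at month 12, Protocol 10.7.2 keeps her out of long-term follow-up. If the removal was for a device problem, q exceeds p and the understatement exceeds f. Changing the denominator removes the dilution but not this selection.

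**The case against.** The strongest reply is that neither document sets out how the 12-36 month incidence is calculated. SAP section 13, the part written for this phase, names no population. On that view the ITT denominator is only inferred from a general rule, and the firmer finding is an undefined denominator. Section 13 is indeed silent. But the rule in SAP 12.5 covers all safety analyses without exception, and Protocol 13.5.6 assigns this endpoint to ITT by name. A programmer following the text would divide by ITT, and the remedy is the same on either reading.

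Other points on that side, and what stands:
- **The per-protocol set uses observed data.** True (Protocol 13.2.2, SAP 6.1.1), so it is less diluted. It also drops women with low treatment compliance or major violations, so it does not replace an at-risk safety set.
- **Re-entrants' gap is partly closed.** This stands. The consent visit takes a medical and surgical history since month 12 (Protocol 11.4.1), and the schedule marks adverse event collection there. A reader might infer that late re-entrants are necessarily treated as fully observed with their earlier events lost; the documents do not support that.
- **The affected group may be small.** This stands. The re-consent route concerns only women who exited before the long-term visits were added, and their number is not given.
- **Missing follow-up would be visible.** Partly. SAP 12.1 provides accountability by visit and a listing of dropouts, from which an approximate rate among those followed could be worked out. It does not ask for counts of women who declined or were ineligible for re-entry.
- **The endpoint is descriptive.** This stands. Periodic safety reports and annual safety board review also continue. A reader might infer that an upper confidence bound would be falsely tight, but the plan specifies no such bound for adverse events.

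**Conclusion.** The concern holds in conditional form. The written rule puts the 12-36 month related-event incidence on all women with a skin incision, as a crude percentage, with no at-risk denominator. It understates late harm in proportion to the share of women not observed after month 12: 10-40% in relative terms for f of 10-40%, and nothing at f = 0. This assumes equal risk in observed and unobserved women. The assumption is least secure for women whose implant was removed, either because they are no longer exposed or because the removal itself reflects harm.

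A reader might infer that late device harm is in fact understated by a material amount. The documents do not support that, because f is unknown and could be small; the percentages above are illustrations, not estimates. The primary and secondary efficacy conclusions are unaffected. The change is worth making before long-term results are tabulated, so that the denominator is not chosen after the data are seen.

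**What to change.** In SAP 12.5 and section 13:

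1. List the 12-36 month incidence of procedure- or device-related events as an endpoint. Base it on ITT women with at least one adverse event assessment after month 12. Women explanted after month 12 stay in this set and are counted.
2. Add events per 100 woman-years. Time runs from month 12 to last contact, or from the long-term consent visit for re-entrants whose events since exit are not recovered there.
3. Show the crude ITT percentage beside these figures.
4. Report how many women exited at month 12, re-consented, declined or were ineligible, giving separately those whose implant had been removed. Report also how many ITT women had no observation after month 12. This shows the selection that a new denominator cannot correct.
5. Keep ITT for implantation to month 12.

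The cost is SAP wording, one more column in the long-term adverse event table and a short accountability table. No new visits are needed. The reported rate may look less favourable.
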